The Mucosal Immunology and Vaccinology Laboratory (MIVL) at the icddr,b is a Biosafety Level 2 (BSL2) facility with internal and external quality assurance carried out for tests. All SOPs for studies are updated frequently to meet study requirements. The laboratory is equipped with ten biohazard safety hoods for the processing of biological samples and for maintaining sterile conditions for specimen processing. For the fractionation of samples one bead beater is available, and for the separation of samples temperature-controlled tabletop centrifuges, high-speed centrifuges (Beckman) and ultracentrifuge (Beckman Coulter High Speed Centrifuge) are also available. Three Incubators with carbon-dioxide gas attachment for the study of B-cell and T-cell responses, four incubators and two shaker incubators for bacterial culture and Enzyme Linked Immunosorbent Assay (ELISA) are present. There is a cryostat for sectioning of frozen sections and a microtome for paraffin sections. Five ELISA readers (EON) linked to computers for determining antibody responses in study samples are present. Facilities for Enzyme Linked Immunosorbent Spot (ELISPOT) and Antibody in Lymphocyte Supernatant (ALS) assays are available. The Cellular Technology Limited (CTL) automatic immunospots counters as well as stereomicroscopes for enumeration of Antibody Secreting Cells (ASCs) are also available. There are facilities for carrying out the extraction of lymphocytes from gut biopsies. Two conventional polymerase chain reaction (PCR) machines, two real time PCR (RT-PCR) machines, and one TaqMan PCR machine are available for any preferable gene amplification. Two Luminex machine of xMAP company (Magpix and Intelliflex) and four Fluorescence-Activated Cell Sorting (FACS) machines (two Acuri, Fusion, and Aria III) are present for high throughput analysis. We have liquid nitrogen sample storage facility. In addition, facilities for carrying out intestinal lavages and fecal extracts are used for assessing mucosal antibody responses. There are several refrigerators and freezers maintained at 4°C, -20°C, and -80°C used for storing specimens from vaccine trials and other infectious disease studies.

Literature Cited

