- To evaluate the effectiveness of typhoid conjugate vaccine (TCV) against blood culture-confirmed typhoid fever stratified by age groups (6 months to <2 years, 2 to 4 years, 5 to 15 years)
- To evaluate the effectiveness of typhoid conjugate vaccine (TCV) against blood culture-confirmed typhoid fever stratified by the period of follow-up (first and second six months) after vaccination
- To determine the immunogenicity of TCV in a subset of participants, stratified by age groups (6 months to <2 years, 2 to 4 years, 5 to 15 years)

f. Methods:

This is a prospective closed cohort, open-label, phase III effectiveness study using a test-negative design of a typhoid conjugate vaccine, ZyVac® TCV (purified Vi capsular polysaccharide of *Salmonella* Typhi conjugated to tetanus toxoid as carrier protein), manufactured by Zydus Lifesciences Limited. The study will be conducted in a closed cohort population among children aged 6 months to 15 years residing in wards 5, 6, 7, 48, 49, 50, 63, 71, and 72 of Dhaka South City Corporation (DSCC). The targeted number of age-eligible children in the study area is ~92,000 among them ~60,000 will be vaccinated. A subset of the first 600 consenting participants will be selected by age strata (6 months to <2 years, 2-4 years, 5-15 years) for enrollment in the immunogenicity study with an additional three follow-up visits. Diary cards will be used to collect adverse events (AEs) following immunization (AEFI) data up to day 7 for a subset of active follow-up of the first 600 vaccinated participants. Participants not in this subset will be encouraged to go to the 'Adverse Event Monitoring Cell' at the Maniknagar field office. Data on serious adverse events (SAEs) will be reported for six months after vaccination. All study updates including AEs and SAEs will be reported to the data safety and monitoring board (DSMB) and sponsor. Passive surveillance for typhoid fever will be carried out in the Maniknagar field office and Mugda Medical College and Hospital in the catchment area among the age-eligible children.

g. Outcome measures/variables:

Primary outcome
Blood culture-confirmed typhoid fever

Secondary outcome
Anti-Vi-IgG antibody concentration
Blood culture-confirmed paratyphoid fever

Description of the Research Project

Hypothesis	to	be	tested:
------------	----	----	---------

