The vaccine is packaged as a pre-filled 2.5ml 5-dose vial. It will be administered as an intramuscular injection preferably in the anterolateral aspect of the middle thigh for younger children, or the upper arm for older children with aseptic precautions.

Supply

The Vi-TCV vaccine (ZyVac® TCV) will be provided by Zydus Lifesciences Limited.

Storage

The Vi-TCV study vaccine will be stored at 2° to 8° C in a temperature monitored icddr,b cold room facilities, when not in use for daily activities. The vaccines will be stored in temperature-monitored refrigerators or cool boxes, when in use for daily activities. Each vial will be labeled with a "vaccine vial monitor"(VVM); a temperature-sensitive dot that provides an indication of the cumulative heat to which the vial has been exposed. It warns the end-user when exposure to heat is likely to have degraded the vaccine beyond an acceptable level and should not be used.

Special precautions for storage

Store at 2°C to 8°C.

Do not freeze. Discard if frozen.

Keep out of reach of children.

Shake gently before use.

Do not use the vaccine after the expiration date shown on the label

Accountability of the study vaccine

The vaccines will be shipped to a central storage facility in Bangladesh and passed through customs. It will then be transported and distributed to local vaccination sites whilst maintaining the cold chain (aiming for a temperature between 2°-8°C). The number of doses of study vaccines that are received, used, and wasted will be documented daily during the study and checked weekly.

Adverse events following immunization

After administration of the study vaccine, participants will be observed closely for at least 30 minutes for any immediate hypersensitivity reactions or any other adverse events (AEs). All details will be recorded in the CRF.

Adverse events follow up (Day 7, -1/+7):

A subset of 600 participants will be selected for active surveillance follow-up and the immunogenicity sub-study. A diary card will be given to each participant on the day of vaccination. Participants will be contacted by telephone or inperson after seven days of vaccination for follow-up and to record any adverse events following immunization (AEFI).

The selection of these participants will be age-stratified (6 months to <2 years, 2-4 years, and 5-15 years) with an allocation of 200 in each age stratum.

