Parents of participants not in this subset will be encouraged to go to the 'adverse event monitoring cell' at the Maniknagar field office which will have a medical doctor and also available on-call 24 hours a day for adverse event monitoring throughout the whole vaccination period + 7 days.

Information will include:

- Verbal reconfirmation of consent for participation in the study.
- Report from parent/guardian of adverse events related to vaccination and use of medications following vaccination-
- After administration of TCV, solicited local AEs (pain, redness, swelling and induration) and solicited systemic AEs (fever, nausea, vomiting, diarrhea, headache1, malaise1, myalgia1, arthralgia1, abnormal crying2, loss of appetite2, drowsiness2 and irritability2 (1: applicable for subjects aged ≥2 years; 2: applicable for subjects <2 years of age)) will be recorded for 7 days after vaccination. Unsolicited (other) AEs will be recorded for 28 days after vaccination.
- Reiteration of contact details and instructions to attend the Maniknagar field office in case of fever (≥2 days and/or temperature ≥38°C at presentation).

Safety reporting:

Definitions

Below are the various categories of adverse events following immunization (AEFIs).

Adverse event (AE)	Any untoward medical occurrence in a participant to whom a medicinal product has been administered, including occurrences that are not necessarily caused by or related to that product.								
Adverse reaction (AR)	An untoward and unintended response in a participant to an investigational medicinal product which is related to any dose administered to that participant. The phrase "response to an investigational medicinal product" means that a causal relationship between a study medication and an AE is at least a reasonable possibility, i.e. the relationship cannot be ruled out. All cases judged by either the reporting medically qualified professional or the								
	sponsor as having a reasonable suspected causal relationship to the study medication qualify as adverse reactions.								
Serious adverse event (SAE)	 A serious adverse event is any untoward medical occurrence that: results in death is life-threatening requires inpatient hospitalization or prolongation of existing hospitalization results in persistent or significant disability/incapacity consists of a congenital anomaly or birth defect. 								

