	Other 'important medical events' may also be considered serious if they jeopardize the participant or require an intervention to prevent one of the above consequences.								

NOTE: The term "life-threatening" in the definition of "serious" refers to an
event in which the participant was at risk of death at the time of the event; it does not refer to an event which hypothetically might have caused death if it
were more severe.

Causality

The relationship of each adverse event to the study medication must be determined by a medically qualified individual according to the following definitions:

Related: There is suspicion that there is a relationship between the study vaccine and the AE (without determining the extent of probability); there is a reasonable possibility that the study vaccine contributed to the AE

Not related: There is no suspicion that there is a relationship between the study vaccine and the AE; there are other more likely causes and administration of the study vaccine is not suspected to have contributed to the AE

Procedures for recording adverse events

From vaccination through day 7

After administration of TCV, solicited local AEs (pain, redness, swelling and induration), solicited systemic AEs (fever, nausea, vomiting, diarrhea, headache1, malaise1, myalgia1, arthralgia1, abnormal crying2, loss of appetite2, drowsiness2 and irritability2 (1: applicable for participants aged ≥2 years; 2: applicable for participants <2 years of age)) for 7 days after vaccination. Unsolicited (other) AEs will be recorded for 28 days after vaccination.

For injectable vaccines, the local signs and symptoms to be documented usually include, as a minimum, pain, redness, and swelling at the injection site in all age groups. Measuring devices of various types may be used to record the extent of redness and swelling. Fever will be documented using digital thermometers and axillary temperature will be determined. For subjective symptoms (for example, fatigue and myalgia) following scoring system will be considered.

The following scoring system will be used for grading of severity:

Parameter	Mild	Moderate	Severe	Potentially life threating

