Injection site pain (pain without touching) Or Tenderness (pain when area is touched)	Pain/tenderness causing no or minimal limitation of use of limb	Pain/tenderness limiting use of limb OR Pain/tenderness causing greater than minimal interference with usual social & functional activities	Pain/tenderness causing inability to perform usual social & functional activities	Pain/tenderness causing inability to perform basic self-care function OR Hospitalization (other than emergency room visit) indicated for management of pain/tenderness
Fever	37.7 – 38.6°C	38.7 – 39.3°C	39.4 – 40.5°C	> 40.5°C
Malaise	Symptoms causing no or minimal interference with usual social &	Symptoms causing greater than minimal interference with usual social &	Symptoms causing inability to perform usual social & functional activities	Incapacitating fatigue/ malaise symptoms causing inability to

	functional activities	functional activities		perform basic self- care functions
Myalgia	Muscle pain causing no or minimal interference with usual social & functional activities	Muscle pain causing greater than minimal interference with usual social & functional activities	Muscle pain causing inability to perform usual social & functional activities	Disabling muscle pain causing inability to perform basic self-care functions

All adverse events related to vaccination, as judged by a medically qualified investigator, occurring during the first 7 days post-vaccination that are observed by the study team/investigator or reported by the participant's parent/guardian, will be recorded on the CRF. The information will be collected both passively and actively.

For active surveillance of a subset of 600 participants, information will be actively collected via phone calls or home visits. Parents of participants not in this subset will be encouraged to go to the 'Adverse Event Monitoring Cell' at the Maniknagar field office which will have a medical doctor and also available on-call 24 hours a day for adverse event monitoring throughout the whole vaccination period + 7 days.

The following information will be recorded: description, date of onset and end date, severity, assessment of relatedness to study medication, and action taken. Follow-up information should be provided as necessary.

The severity of events will be assessed on the following scale: 1 = mild, 2 = moderate, 3 = severe, 4 = Potentially life-threatening

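### The CRF rule for non-serious adverse events (vaccine-related, first 7 days) conflicts with the protocol's own 28-day window for unsolicited events, which carries no relatedness condition

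*Protocol*

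**What the plan says.** All references are to the protocol.

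- **Adverse events following immunization (30-minute observation).** Staff watch for "any immediate hypersensitivity reactions or any other adverse events (AEs). All details will be recorded in the CRF". There is no relatedness condition.
- **Adverse events follow up (Day 7, -1/+7).** The 600-child subset is contacted "after seven days of vaccination for follow-up and to record any adverse events following immunization (AEFI". The items listed for that contact include "Report from parent/guardian of adverse events related to vaccination and use of medications following vaccination", and the next item says "Unsolicited (other) AEs will be recorded for 28 days after vaccination". The first is limited to related events and gives no window. The second gives a window and no relatedness condition.
- **Safety reporting, Definitions.** An adverse event is defined broadly, "including occurrences that are not necessarily caused by or related to that product". Adverse reactions are defined separately.
- **Causality.** A medically qualified person must determine the relationship for each adverse event, and one of the two categories is not related.
- **Procedures for recording adverse events.** Under the heading "From vaccination through day 7", the 28-day sentence appears a second time. Later under the same heading comes the CRF rule: "All adverse events related to vaccination, as judged by a medically qualified investigator, occurring during the first 7 days post-vaccination", whether observed by staff or reported by a parent, go on the CRF. The data items to be recorded include an assessment of relatedness.
- **Throughout the study period.** This next recording section deals only with serious adverse events, which are recorded for the whole study.
- **Project Summary, Methods.** "Diary cards will be used to collect adverse events (AEs) following immunization (AEFI) data up to day 7" in the subset of 600.
- **Immunogenicity study.** The visit at D30/+7 lists confirmation of participation, blood collection, and contact details with fever instructions.
- **Monitoring cell, for vaccinees outside the subset.** Parents are encouraged to report to it. It runs until 7 days after the vaccination period ends.

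**The concern.** Once the 30-minute observation is over, the only explicit statement of which non-serious events reach the CRF is the related-and-7-day rule. A site that works from that sentence would produce an unsolicited-event summary cut at day 7 and screened for relatedness before recording. A site that works from the 28-day sentences would produce a longer, unscreened record. The planned safety analysis is descriptive, so its content is simply whatever was recorded. An analysis plan can choose how to tabulate the events but cannot recover those that never reached the CRF.

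The collection schedule adds a second difficulty. If the report describes a 28-day window but the procedures reach only part of it, the denominator of observed time is misdescribed.

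**Working it through.** The plan gives no figure to reproduce. The check compares the statements and then counts days.

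**Statements side by side**

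| Place | Window | Relatedness condition |
|---|---|---|
| 30-minute observation | 30 minutes | none |
| Follow-up contact, first relevant item | not stated | related only |
| Follow-up contact, unsolicited events | 28 days | none |
| Recording section, unsolicited events | 28 days | none |
| Recording section, CRF rule | 7 days | judged related |
| Definition of adverse event | – | expressly includes unrelated events |
| Causality section | – | each event classified, including as not related |
| Items recorded per event | – | relatedness is a data item |

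The day-7 heading does not resolve the conflict, because one 28-day sentence sits under that same heading and the other sits under the day-7 follow-up heading. The next recording section covers serious events only, so no separate recording section takes over for non-serious events on days 8 to 28. If relatedness decided entry to the CRF, the relatedness item and the not-related category would have no use for non-serious events after the first 30 minutes.

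**Scheduled collection in the 600-child subset**

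- Contact at day 7, -1/+7: 7 − 1 = day 6 to 7 + 7 = day 14.
- Diary card: to day 7.
- Next visit, D30/+7: day 30 to 30 + 7 = day 37, with no adverse-event item listed.
- Latest possible contact (day 14): 28 − 14 = 14 days remain, 14/28 = 50%.
- Contact on day 6 or 7, with the diary running to day 7: 28 − 7 = 21 days remain, 21/28 = 75%.

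So 14 to 21 of the 28 days have no described diary or scheduled contact. Days 15 to 28 are in that position for every child in the subset.

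**Passive cell, other vaccinees**

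Let a child be vaccinated *d* days before the vaccination period ends. The cell is open until that child's day *d* + 7. Cover to day 28 needs *d* + 7 ≥ 28, so *d* ≥ 21. A child vaccinated on the last day (*d* = 0) has the cell for 7 of 28 days (25%).

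**If the one-month visit were used**

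It falls 30 − 28 = 2 to 37 − 28 = 9 days after day 28. The look-back to the preceding contact is 30 − 14 = 16 to 37 − 6 = 31 days.

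**The case against.** The other side has good arguments, and several of them stand.

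- **The CRF rule does not say only.** Read with the causality section, the relatedness item and the follow-up contact that records any event, a careful site might not screen events at all. This stands: the statements are inconsistent, not mutually exclusive. It does not remove the defect, because the explicit CRF rule still says something different from the sections around it.
- **A reader might infer that nothing reaches days 15 to 28.** The document does not support that. The monitoring cell has a doctor, is on call around the clock, and covers all 28 days for children vaccinated early enough. What is missing is a scheduled contact and a passive route that covers every child.
- **A reader might infer that 28 days of active follow-up was promised and not delivered.** It was not promised. A recording window is compatible with passive reporting, and the protocol says that collection is both active and passive. It gives no number or end date for the phone calls or home visits in the subset.
- **A reader might count the gap from day 6 and get 22 days (79%).** That ignores the diary card, which runs to day 7. The upper bound is 21 days (75%).
- **Material is not visible.** The timeline shading and the flow diagram are lost, and the CRFs are not shown. A separate adverse-event form at the one-month visit cannot be excluded. The length of the vaccination period cannot be read, so the share of children short of 28 days of cell cover is unknown, and the 25% figure is the last-day extreme. None of this touches the conflict in wording.

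**Conclusion.** The inconsistency holds and is worth correcting. On window (7 against 28 days) and on scope (judged related against all unsolicited events), the CRF rule disagrees with two other statements of the protocol, and it also disagrees with the protocol's adverse-event definition, its causality rule and its own list of recorded items. On collection, the conclusion is narrower: in the readable text, days 15 to 28 have no scheduled adverse-event contact, and the passive cell covers the full 28 days only for children vaccinated at least 21 days before the vaccination period ends.

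The consequence is confined to the descriptive summary of non-serious events. A reader might extend it to serious events or to the effectiveness estimate. The protocol does not support this: serious events are recorded for the whole study without a relatedness limit, and the effectiveness analysis does not use these data. The number of events that would be missed cannot be derived from the document. The collection part assumes that the hidden timeline and unseen forms add no further adverse-event contact.

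**What to change.** 1. Reconcile the sections on adverse events following immunization, day-7 follow-up and recording procedures to one window and one stated population for unsolicited events.
2. Remove relatedness to vaccination as a condition for recording, both in the list of items for the follow-up contact and in the CRF rule. Use the relatedness item that the protocol already records, so that related events can be tabulated separately.
3. For the 600-child subset and for the other vaccinees, state whether collection after the day-7 contact is active or passive and which days it actually covers. The reported window should match what is collected.

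If active collection to day 28 is intended, an adverse-event question at the existing one-month visit is one option for the subset. It is not a required change, and it would rely on parental recall over 16 to 31 days. Keeping 28 days with openly stated passive reporting after day 7 is equally coherent.

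The cost is wording changes and more unrelated events to code. No additional visit or sample is needed.
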